#### **10.1.9. Study and Site Start and Closure**

The study may be suspended temporarily or terminated prematurely if there is sufficient reasonable cause. Written notification documenting the reason for study suspension or termination will be provided by the Sponsor to Investigators and regulatory authorities. If the study is prematurely terminated or suspended, the Investigator will promptly inform Participants and the IRB and will provide the reasons for the termination or suspension. Participants will be contacted, as applicable, and be informed of changes to Study Visit schedules.

The Sponsor reserves the right to discontinue the study for any safety, ethical, or administrative reason at any time.

---

The Sponsor or designee reserves the right to close a Clinical Site or terminate the study at any time for any reason at the sole discretion of the Sponsor. Study sites will be closed upon study completion.

The Investigator may initiate Clinical Site closure at any time, provided reasonable cause and sufficient notice is given in advance of the intended termination.

Reasons for the early closure of a Clinical Site by the Sponsor or Investigator may include but are not limited to:

- Failure of the Investigator to comply with the protocol, the requirements of the IRB/IEC or local health authorities, the Sponsor's procedures, or GCP guidelines
- Inadequate recruitment of Participants by the Investigator
- Discontinuation of further study drug development

If the study is prematurely terminated or suspended, the Sponsor will promptly inform the Investigators, IRBs, the regulatory authorities, and any CROs used in the study of the reason for termination or suspension, as specified by the applicable regulatory requirements. The Investigator will promptly inform the Participants and should ensure appropriate Participant therapy and/or follow-up.

#### **10.1.10. Publication Policy**

The study will be conducted in accordance with the publication and data sharing policies and regulations as defined in the agreement between the Sponsor and the institution. In addition, this study will be registered at [www.ClinicalTrials.gov](http://www.ClinicalTrials.gov) and in any other protocol registries required by the regions in which the study is conducted, and the results from this study will become publicly available.

None of the data resulting from this study will be allowed to be presented or published in any form by the Investigator or any other person without the prior written approval of the Sponsor.

#### **10.1.11. Insurance**

Matters relating to insurance for this study are to be defined in the agreement between the Sponsor and the institution.

**10.2. Appendix 2. Adverse Events: Definitions and Procedures for Recording, Evaluating, Follow-up, and Reporting****10.2.1. Definition of AE****AE Definition**

- An AE/TEAE is any untoward medical occurrence associated with the use of an investigational product or study procedure in a clinical study Participant, whether or not considered related to the study intervention.
- NOTE: An AE/TEAE can therefore be any unfavorable and unintended sign (including an abnormal laboratory finding), symptom, or disease (new or exacerbated) temporally associated with the use of study intervention or procedure.

**Events Meeting the AE Definition**

- Any abnormal laboratory test results (hematology, or clinical chemistry) or other safety assessments (e.g., ECG, radiological scans, vital signs measurements), including those that worsen from Baseline, considered clinically significant in the medical and scientific judgment of the investigator (i.e., not related to progression of underlying disease).
- Exacerbation of a chronic or intermittent pre-existing condition including either an increase in frequency and/or intensity of the condition.
- New conditions detected or diagnosed after study intervention administration even though it may have been present before the start of the study.
- Signs, symptoms, or the clinical sequelae of a suspected drug-drug interaction.
- Signs, symptoms, or the clinical sequelae of a suspected overdose of either study intervention or a concomitant medication. Overdose per se will not be reported as an AE/SAE unless it is an intentional overdose taken with possible suicidal/self-harming intent. Such overdoses should be reported regardless of sequelae.

**Events NOT Meeting the AE Definition**

- Any clinically significant abnormal laboratory findings or other abnormal safety assessments that are associated with the underlying disease, unless judged by the Investigator to be more severe than expected for the Participant's condition.
- The disease/disorder being studied or expected progression, signs, or symptoms of the disease/disorder being studied, unless more severe than expected for the Participant's condition.
- Medical or surgical procedure (e.g., endoscopy, appendectomy): the condition that leads to the procedure is the AE.
- Situations in which an untoward medical occurrence did not occur (social and/or convenience admission to a hospital).

- Anticipated day-to-day fluctuations of pre-existing disease(s) or condition(s) present or detected at the start of the study that do not worsen.

#### 10.2.2. Definition of TEAE

Treatment-Emergent Adverse Event is defined as:

- An event that emerges during treatment, having been absent at pretreatment, or worsens relative to the pretreatment state, as defined in the E9 Guidance.
- The TEAE is not related to causality / drug relatedness. It may or may not be related to the drug but is considered a TEAE due to its appearance at or after the treatment has been administered.

#### 10.2.3. Definition of SAE

If an event is not an AE per the definition above, then it cannot be an SAE even if serious conditions are met (e.g., hospitalization for signs/symptoms of the disease under study, death due to progression of disease).

An SAE is defined as any untoward medical occurrence that, at any dose:

a. Results in death

b. Is life-threatening

The term “life-threatening” in the definition of “serious” refers to an event in which the Participant was at risk of death at the time of the event. It does not refer to an event, which hypothetically might have caused death, if it were more severe.

c. Requires inpatient hospitalization or prolongation of existing hospitalization

- In general, hospitalization signifies that the Participant has been detained (usually involving at least an overnight stay) at the hospital or emergency ward for observation and/or treatment that would not have been appropriate in the physician’s office or outpatient setting. Complications that occur during hospitalization are AEs. If a complication prolongs hospitalization or fulfills any other serious criteria, the event is serious. When in doubt as to whether “hospitalization” occurred or was necessary, the AE should be considered serious.
- Hospitalization for elective treatment of a pre-existing condition that did not worsen from Baseline is not considered an SAE.

d. Results in persistent disability/incapacity 

• The term “disability” means a substantial disruption of a person’s ability to conduct normal life functions.

• This definition is not intended to include experiences of relatively minor medical significance such as uncomplicated headache, nausea, vomiting, diarrhea, influenza, and accidental trauma (e.g., sprained ankle), which may interfere with or prevent everyday life functions but do not constitute a substantial disruption.

e. Is a congenital anomaly/birth defect
f. Other situations: 

• Medical or scientific judgment should be exercised in deciding whether SAE reporting is appropriate in other situations such as important medical events that may not be immediately life-threatening or result in death or hospitalization but may jeopardize the Participant or may require medical or surgical intervention to prevent one of the other outcomes listed in the above definition. These events should usually be considered serious.

• Examples of such events include invasive or malignant cancers; intensive treatment in an emergency room or at home for allergic bronchospasm, blood dyscrasias, or convulsions that do not result in hospitalization; or development of drug dependency or drug abuse.

#### 10.2.4. Definition of TESAE

Treatment-Emergent Serious Adverse Event is defined as:

• A serious event that emerges during treatment, having been absent at pretreatment, or worsens relative to the pretreatment state, as defined in the E9 Guidance.

• The TESAE is not related to causality / drug relatedness. It may or may not be related to the drug but is considered a TESAE due to its appearance at or after the treatment has been administered.

--

#### 10.2.5. Recording and Follow-Up of AE/TEAE and/or SAE/TESAE

AE and SAE Recording

• When an AE/TEAE or SAE/TESAE occurs, it is the responsibility of the Investigator to review all documentation (e.g., hospital progress notes, laboratory reports, and diagnostics reports) related to the event.

• The Investigator will then record all relevant AE/TEAE or SAE/TESAE information in the eCRF.

• It is not acceptable for the Investigator to send photocopies of the Participant’s medical records to the Sponsor or designee in lieu of completion of the AE/SAE eCRF page.

---

- Instances may arise when copies of medical records for certain cases are requested by the Sponsor or designee. In this case, all Participant identifiers, with the exception of the Participant number, will be redacted on the copies of the medical records before submission to the Sponsor or designee.
- The Investigator will attempt to establish a diagnosis of the event based on signs, symptoms, and/or other clinical information. Whenever possible, the diagnosis (not the individual signs/symptoms) will be documented as the AE/SAE.

#### Assessment of Intensity

The Investigator will make an assessment of intensity for each AE and SAE reported during the study and assign it to 1 of the following categories:

- Mild: An event that is easily tolerated by the Participant, causing minimal discomfort and not interfering with everyday activities.
- Moderate: An event that causes sufficient discomfort and interferes with normal everyday activities.
- Severe: An event that prevents normal everyday activities. An AE that is assessed as severe should not be confused with an SAE. Severe is a category used for rating the intensity of an event; and both AEs and SAEs can be assessed as severe.

An event is defined as “serious” when it meets at least 1 of the predefined outcomes as described in the definition of an SAE, NOT when it is rated as severe.

#### Assessment of Causality

- The Investigator is obligated to assess the relationship between study intervention and each occurrence of each AE/SAE.
- A “reasonable possibility” of a relationship conveys that there are facts, evidence, and/or arguments to suggest a causal relationship, rather than that a relationship cannot be ruled out.
- The Investigator will use clinical judgment to determine the relationship.
- Alternative causes, such as underlying disease(s), concomitant therapy, and other risk factors, as well as the temporal relationship of the event to study intervention administration will be considered and investigated.
- The Investigator will also consult the IB and/or Product Information, for marketed products, in his/her assessment.
- For each AE/SAE, the Investigator **must** document in the medical notes that he/she has reviewed the AE/SAE and has provided an assessment of causality.

- Situations may arise in which an SAE has occurred, and the Investigator has minimal information to include in the initial report to the Sponsor or designee. However, the Investigator must always assess causality for every event before the initial transmission of the SAE data to the Sponsor or designee. Death or hospitalization are not to be specified as an SAE; these are criteria to determine seriousness.
- The Investigator may change his/her opinion of causality in light of follow-up information and send an SAE follow-up report with the updated causality assessment.
- The causality assessment is one of the criteria used when determining regulatory reporting requirements.

#### Follow-up of AEs and SAEs

- The Investigator is obligated to perform or arrange for the conduct of supplemental measurements and/or evaluations as medically indicated or as requested by the Sponsor or designee to elucidate the nature and/or causality of the AE or SAE as fully as possible. This may include additional laboratory tests or investigations, histopathological examinations, or consultation with other health care professionals. New or updated information will be recorded in the originally completed eCRF.
- The Investigator will submit any updated SAE data to the Sponsor or designee within 24 hours of receipt of the information.

#### 10.2.6. Reporting of SAEs/TESAEs

##### SAE Reporting to the Sponsor or Designee via an Electronic Data Collection Tool

- The primary mechanism for reporting an SAE to the Sponsor or designee will be the electronic data collection tool.
- The Site will enter the SAE data into the electronic system as soon as it becomes available.
- After the study is completed at a given Site, the electronic data collection tool will be taken off-line to prevent the entry of new data or changes to existing data.
- If a Site receives a report of a new SAE from a study Participant or receives updated data on a previously reported SAE after the electronic data collection tool has been taken off-line, then the Site can report this information to the Medical Monitor or SAE coordinator by telephone.

---

**10.3. Appendix 3. Grading of Injection Site Reactions**

The following grading guidelines were compiled from sources from the FDA and the National Cancer Institute for Injection Site Reactions (Table 6). Injection sites should be assessed in each upper and each lower limb. A global assessment of all injection sites on each arm and on each leg is to be performed following each treatment. The injection site reaction with the most severe pain/tenderness, erythema/itching/urticaria, and bruising/swelling/bleeding on each arm and on each leg is to be used as the reference point for the injection site reaction grading following each treatment. Note that the most severe pain/tenderness injection site may not be the same injection site reaction with the most severe bruising/swelling/bleeding.

**Table 6: Injection Site Reaction Grading**

Reaction at Injection Site a	Mild (Grade 1)	Moderate (Grade 2)	Severe (Grade 3)	Potentially Life-Threatening (Grade 4)
Pain, tenderness	Mild discomfort to touch, with or without warmth, erythema, itching	Symptoms with or without swelling and/or phlebitis	Symptoms with or without swelling or phlebitis or mild infection	Symptoms with severe infection or tissue injury or ulceration
	Does not interfere with daily activity	Interferes with daily activity	Precludes daily activity	Requires advanced medical and/or surgical care, including intravenous (IV) medications
	No or local treatment	Use of non-narcotic pain reliever	Use of narcotic pain reliever and/or oral antibiotics	
Erythema, itching, urticaria	Mild, localized itching, erythema or urticaria	Symptoms with skin changes beyond local injection site(s)	Symptoms with widespread skin changes	Bronchospasm, anaphylactoid, or anaphylactic reaction
	Does not interfere with activity	Interferes with movement and daily activity	Interferes with daily activity	Requires advanced medical care, including IV medication
	Use of topical treatment	Use of NSAIDs and/or antihistamines	Use of oral steroids or immuno-suppressives	
Bruising, swelling, bleeding	Mild, localized swelling, ecchymosis or hematoma	Moderate ecchymosis or hematoma	Extensive ecchymoses, large hematoma	Hypotension, life-threatening consequences
	Does not interfere with activity	Interferes with daily activity	Precludes activity	Requires transfusion, urgent intervention
	No treatment	Requires leg elevation, conservative treatment	Requires minimally invasive drainage	

Abbreviations: NSAID = non-steroidal anti-inflammatory drugs

a Injection site reactions are a category of AESIs and should be recorded as AEs using these grading guidelines.

---

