The following tables will be presented:

- Summary of TEAE (Table 14.3.1.1)

QMD Ref: Worldwide-TMP-ST-005-7.0 Effective: 12Aug2019	Governing QMD: Worldwide-SOP-ST-001
Confidentiality Statement	

This document is the property of Worldwide Clinical Trials Inc. and may not be duplicated, copied, altered or removed from company without prior approval from Worldwide Quality Assurance or in compliance with Worldwide Standard Operating Procedures.

Worldwide Clinical Trials Controlled Quality Management Document			
 WORLDWIDE CLINICAL TRIALS	Sponsor:	Helixmith Co., Ltd.	
	Protocol Number:	VMALS-002-2	
STATISTICAL ANALYSIS PLAN VERSION 3.0			

- TEAEs organized by SOC and PT (Table 14.3.1.2)
- TESAEs organized by SOC and PT (Table 14.3.1.3)
- TEAEs organized by SOC and PT and Maximum Severity (Table 14.3.1.4)
- TEAEs organized by SOC and PT and Maximum Relationship (Table 14.3.1.5)
- TESAEs organized by SOC and PT and Maximum Severity (Table 14.3.1.6)
- TESAEs organized by SOC and PT and Maximum Relationship (Table 14.3.1.7)
- Incidence Injection site reactions by SOC and PT (Table 14.3.1.8)
- Incidence of clinically significant laboratory values (Table 14.3.1.9)
- AESIs organized by SOC and (Table 14.3.1.10)
- TEAEs leading to study discontinuation by SOC and PT (Table 14.3.1.11)
- TESAEs leading to study discontinuation by SOC and PT (Table 14.3.1.12)
- TEAEs leading to study drug withdrawal by SOC and PT (Table 14.3.1.13)
- TESAEs leading to study drug withdrawal by SOC and PT (Table 14.3.1.14)
- TEAEs related to study medication by SOC and PT (Table 14.3.1.15)
- TESAEs related to study medication by SOC and PT (Table 14.3.1.16)

The following listings will be provided:

- All AEs (Listing 16.2.7.1)
- AESIs (Listing 16.2.7.2)
- TESAEs (Listing 16.2.7.3)
- Injection Site Reactions (Listing 16.2.7.4)
- TEAEs leading to study discontinuation (Listing 16.2.7.5)
- TEAEs related to study medication (Listing 16.2.7.6)
- TESAEs leading to death (Listing 16.2.7.7)

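### In Table 6 the activity criterion for erythema, itching and urticaria does not rise from Grade 2 to Grade 3, so the severity of a skin reaction (not ISR incidence) can depend on which line is read

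*Protocol*

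**What the plan says.** Protocol Section 10.3 (Appendix 3) asks for a global assessment of each arm and each leg after every treatment. The worst reaction of each of three types (pain/tenderness, erythema/itching/urticaria, bruising/swelling/bleeding) is the reference for grading. Table 6 then gives, for each type, several lines of criteria under columns headed Mild (Grade 1) to Potentially Life-Threatening (Grade 4).

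In the erythema/itching/urticaria row, the activity line reads "Interferes with movement and daily activity" at Grade 2 and "Interferes with daily activity" at Grade 3. In the other two rows the Grade 3 entries are "Precludes daily activity" (pain) and "Precludes activity" (bruising).

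Footnote a to the table says: "Injection site reactions are a category of AESIs and should be recorded as AEs using these grading guidelines".

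Section 10.2.5, Assessment of Intensity, requires every AE and SAE to be placed in one of three categories and makes no exception for ISRs. Its middle category is "Moderate: An event that causes sufficient discomfort and interferes with normal everyday activities". Its Severe category is for events that stop the participant's ordinary activities.

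The primary ISR endpoint (Protocol Section 9.3.1, SAP Section 3.1) is incidence. SAP Section 6.14.1 tabulates it by SOC and PT in Table 14.3.1.8. Severity enters the planned tables through maximum severity of TEAEs (Table 14.3.1.4) and TESAEs (Table 14.3.1.6). ISRs are also listed individually (Listing 16.2.7.4).

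**The concern.** A grading scale works only if each step up demands something worse. Here the Grade 3 activity criterion is met by every reaction that meets the Grade 2 criterion, and by some milder ones too. A site that follows the activity line literally can therefore call a milder skin reaction Severe and a worse one Moderate.

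Two gaps make this harder to resolve at the site. Appendix 3 fixes which reaction is graded, but not which line decides when the lines of a row disagree. And an ISR recorded as an AE falls under both a four-grade scale and a three-category scale.

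At stake is the meaning of ISR severity in a trial whose primary objective is safety and whose safety analysis is purely descriptive. Without formal testing, readers rely on the categories having one meaning.

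**Working it through.** The documents give no power or sample-size figure that depends on this point, so the check is a comparison of criteria.

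**Step 1. Activity line, by row and grade (Table 6) and by category (Section 10.2.5).**

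| Source | Mild / Grade 1 | Moderate / Grade 2 | Severe / Grade 3 | Rises? |
|---|---|---|---|---|
| Pain, tenderness | no interference | interferes | precludes | yes |
| Bruising, swelling, bleeding | no interference | interferes | precludes | yes |
| Erythema, itching, urticaria | no interference | interferes with movement **and** daily activity | interferes with daily activity | **no** |
| AE intensity, Section 10.2.5 | no interference | interferes | prevents | yes |

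The words "Interferes with daily activity" stand at Grade 2 in the pain and bruising rows and at Grade 3 in the erythema row.

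**Step 2. The inversion.** Take two skin reactions. A interferes with daily activity but not movement. B interferes with both, so it is at least as bad as A. Read literally, A fails the Grade 2 activity line and meets the Grade 3 line. B matches the Grade 2 line word for word. B can thus be graded below A.

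**Step 3. The other lines of the same row.** Extent goes from localized, to beyond the injection site, to widespread. Treatment goes from topical, to NSAID and/or antihistamine, to oral steroid or immunosuppressive. Both rise with grade. The defect is one line of one row. Because the neighbouring cells sit in their expected columns, a fault in reading the PDF is unlikely, though the printed page should be checked.

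**Step 4. Worked case.** Erythema spreads beyond the injection site but is not widespread, and it interferes with daily activity but not movement.
- Extent line: Grade 2.
- Activity line: Grade 3 (Severe).
- Section 10.2.5: Moderate.

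Nothing in Appendix 3 says which line prevails. The same gap exists in the pain row: pain that does not interfere with activity but is treated with a non-narcotic analgesic is Grade 1 by activity and Grade 2 by treatment.

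**Step 5. Grade 4.** Table 6 has four grades and Section 10.2.5 has three categories. SAP Section 6.14.1 assigns maximum severity when severity is missing, without saying whether that means Severe or Grade 4 for an ISR.

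**Step 6. Size in the tables.** With the planned 12:6 allocation, one reclassified participant moves the severe-ISR percentage by 1/12 = 8.3 points (Engensis) or 1/6 = 16.7 points (Placebo). There are up to 6 visits x 4 limbs x 3 reaction types = 72 gradings per participant, of which 6 x 4 x 1 = 24 use the disordered row. The documents give no rate of activity-limiting itching or erythema, so an expected number of discordant gradings cannot be calculated.

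**The case against.** The strongest reply is that the defect is small and mostly answered by the protocol itself. Table 6's own column headings equate Grades 1 to 3 with Mild, Moderate and Severe, and footnote a is the specific rule for ISRs, so its natural reading is that Table 6 governs over the general scale. That stands for Grades 1 to 3. An express sentence would remove doubt, but the two scales are not in open conflict across the board. It does not repair the disordered line, and it leaves Grade 4 without a category. Grade 4 events would ordinarily meet the seriousness criteria and so also appear among the TESAEs.

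A reader might infer that the primary ISR endpoint is compromised. It is not: any ISR counts whatever its grade, no severity threshold drives an analysis, and no formal safety testing is planned.

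A reader might also infer that discordant gradings are likely because there are so many. The counts do not show this, and 8.3 and 16.7 points are simply the weight of one participant on any item. What evidence there is points the other way. The Protocol synopsis reports 26 ISRs in the Phase 1/2 ALS study, all mild (Grade 1), and Section 2.2.6.1 says ISRs there were limited to pain and/or bruising. Section 2.3.1 describes itching and erythema across the programme as mild and transient. That study's grading scale is not stated, and its 256 injections per participant compare with 6 x 128 = 768 here, so this is reassurance, not proof.

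Raters are blinded (Protocol Sections 6.3.2 and 6.3.3), so inconsistent reading would add noise, and nothing suggests that it would favour an arm. With 18 participants, every ISR can be read in the listings. Site guidance or eCRF instructions, which are not in the documents, may already say which line governs.

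**Conclusion.** The activity line of the erythema/itching/urticaria row is wrong as printed, because it does not rise from Grade 2 to Grade 3. A skin reaction can be graded Moderate or Severe depending on the line read, and that grade passes into Tables 14.3.1.4 and 14.3.1.6 and the listings. The missing rule for conflicting lines and the unmapped Grade 4 are supporting points that need clarification.

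The point is minor. ISR incidence is unaffected, the rest of that row is ordered, the activity lines of the other two rows agree with Section 10.2.5, and the frequency is unknown and probably low. The documents do not support calling the whole scale inverted. Nor do they show which of the two cells is the slip: the reference to movement at Grade 2 could be the error as easily as the wording at Grade 3.

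The conclusion assumes that the table text is as printed in the protocol and that no separate site instruction already resolves it.

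**What to change.** Reconcile Section 10.2.5, the text of Appendix 3 and Table 6 in three places.

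1. Revise the erythema/itching/urticaria activity line so that it rises with grade, as it does in the other two rows. Which cell changes, and the wording, are for the sponsor.
2. State in Appendix 3 which criterion governs when the lines of a row point to different grades. Do this together with item 1: a highest-criterion rule applied to the present text would make any skin reaction that interferes with daily activity Grade 3.
3. State in Section 10.2.5 that the Table 6 grade is the AE intensity for ISRs. Say in the SAP how Grade 4 appears in Tables 14.3.1.4 and 14.3.1.6, and what maximum severity means for an ISR with missing severity.

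The cost is a few sentences in the protocol and SAP and matching eCRF guidance, with no new visit or assessment. Some reactions may be graded differently from how they would be under the present text. Showing maximum grade in Table 14.3.1.8 would be a presentational option; the correction does not depend on it.
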